# **Intervention Condition 1 (Visit 3, Day 5 to 360)**

- Obtain and document child assent from child subject on study assent form (if child was not present at Visit 1 and is able to complete/understand form).
- Child completion of study questionnaires (if child was not present at Visit 1 and is able to complete/understand form) to obtain information about child perception of dental anxiety.
- Obtain parent-report of current medications of child.
- First dental cleaning will occur, based on randomization of participant into RDE vs. SADE condition.
- Prior to first cleaning, complete Dental Room Set-Up Checklist to ensure fidelity with environment.
- Dentist will photograph child's teeth prior to cleaning.
- Concurrent with the first dental cleaning, record results of dental cleaning on Oral Health Indices Form, complete Visit Completion Form and EDA Flag Form, and collect videorecording and EDA data. (Complete list of measures to be completed are listed in the Schedule of Events in Appendix A; see CRFs 13, 25-26)
- Following administration of dental cleaning:
  - Dentist will photograph child's teeth inside the child's mouth using an intraoral camera.
  - We will obtain dentist's perception of subject's behavior throughout the dental cleaning [Behavioral Indices Form (Anxiety and Cooperation Scale and Frankl Scale); See CRF 14]; complete Usual Dental Care and Planning Form (CRF 15).
  - We will administer child questionnaires (Faces Pain Scale Revised, Dental Sensory Sensitivity Scale, and if in the SADE environment, the Child SADE Acceptance Form; See CRFs 17-19).
  - If in the SADE environment, we will administer the Parent SADE Acceptance Form (See CRF 20).
  - If, based on the Clinical Examination, the child has any dental needs, the dentist will complete the Dental Letter to Parents (Appendix K). A copy will be given to the parent and a copy will be placed in the child's chart and his/her dental findings will be recorded in the child's e-record if the child is a CHLA dental patient.

Note-1: Scoring of intra-oral photographs will take place following the dental cleaning at CHLA by a trained dentist (CRF 16: Quality of Care Recording Form). Coding of video-recordings and EDA recordings will occur off-site (at the designated lab space of the Health Sciences Campus of the University of Southern California) at a later time. (CRFs 22-23: Children's Dental Behavior Rating Scale & Scored EDA Form)

*Note-2*: Lighting for the intra-oral photographs is provided by the camera inside the mouth and, according to the company representatives, will be comparable in both SADE and RDE conditions.

 Record and report unanticipated problems as reported by subject/parent or observed by investigator/dental staff (See CRF 27: Unanticipated Problem Form).

# Intervention Condition 2 (Visit 4, Day 125-450)

- Update parent-report of current medications of child.
- Second dental cleaning will occur, based on randomization of participant into RDE vs. SADE environment.
- Dentist will photograph child's teeth prior to cleaning.
- Concurrent with the second dental cleaning, record results of dental cleaning on Oral Health Indices Form, complete Visit Completion Form and EDA Flag Form, and collect video-recording and EDA data. (Complete list of measures to be completed are listed in the Schedule of Events in Appendix A; see CRFs 13, 25-26)
- Following administration of dental cleaning:
  - Dentist will photograph child's teeth.
  - Obtain dentist's perception of subject's behavior throughout the dental cleaning [Behavioral Indices Form (Anxiety and Cooperation Scale and Frankl Scale); See CRF 14]; complete Usual Dental Care and Planning Form (CRF 15).
  - Administer child questionnaires (Faces Pain Scale Revised, Dental Sensory Sensitivity Scale, and if in the SADE environment, the Child SADE Acceptance Form; See CRFs 17-19).
  - If in the SADE environment, we will administer the Parent SADE Acceptance Form (See CRF 20).
  - o If, based on the Clinical Examination, the child has any dental needs, the dentist will complete the Dental Letter to Parents (Appendix K). A copy will be given to the parent and a copy will be placed in the child's chart and his/her dental findings will be recorded in the child's e-record if the child is a CHLA dental patient.

Note-1: Scoring of intra-oral photographs will take place at a later date following the dental cleaning at CHLA by a trained dentist (CRF 16: Quality of Care Recording Form). Coding of video-recordings and EDA recordings will occur off-site (at the designated lab space of the Health Sciences Campus of the University of Southern California) at a later time (CRFs 22-23: Children's Dental Behavior Rating Scale & Scored EDA Form).

*Note-2*: Lighting for the intra-oral photographs is provided by the camera inside the mouth and, according to the company representatives, will be comparable in both SADE and RDE conditions.

Note-3: (COVID-19 modifications) At the beginning of the COVID-19 pandemic (March 2020), all research activities were discontinued. At that time, all participants had been recruited and completed Visits 1-3. Twenty-five participants had not completed the final visit (second dental cleaning). Once permission to resume research activities is provided by USC and CHLA we will adhere to all COVID-19-related guidelines and regulations from CHLA and USC. To protect the health and safety of patients and staff during the COVID-19 pandemic, CHLA now requires participants take a COVID-19 test 72 hours prior to a scheduled dental cleaning visit. This will require an extra visit for our participants. Thus, for the remaining 25 participants who will be completing their second dental visit, the study team will inform the parent/legal guardian of the COVID-19 test (until it is no longer a requirement at CHLA) and the rideshare option for both the COVID-19 testing and the dental cleaning visit. The study team will follow the most current CHLA procedures and guidelines and as changes are made, we will abide by the most current CHLA procedures and guidelines.

 Record unanticipated problems as reported by subject/parent or observed by investigator/dental staff (See CRF 27: Unanticipated Problem Form).

## 7.4 Final Study Visit

## Final Study Visit = Visit 4 (125-450 days)

This study's final visit will be the second dental cleaning visit at CHLA; there are no special procedures or evaluations (other than those noted in Visit 4 above) to be completed after the second dental cleaning.

Upon completion of the second dental cleaning, participants and parents will be informed that the study is complete and oral care will return to as it was prior to the study (e.g., continue recalls at CHLA every 6 months if CHLA client, or return to other dentist if not a CHLA client) with no further compensation or access to the adapted environment. Parents will again be given contact information of research team members in the case that they have any questions or want to contact the researchers (also located on the signed and dated copy of the consent form). Parents will be instructed to contact the research team if any AEs or SAEs occur following Visit 4. If appropriate, a member of the research team will follow-up via phone call to ensure that any AE/SAEs have been resolved. Individual participants will not be informed of study results.

### 7.5 Withdrawal Visit

There will not be a withdrawal visit and no evaluations are specifically required for the final visit as the final visit is the second dental cleaning visit (Visit 4 above).

We will make every attempt to ensure that each child gets two dental cleanings, one in each condition (SADE and RDE). Missed appointments will be rescheduled, as many times as necessary up to eight months following the child's first dental cleaning (with participants receiving priority scheduling), extra reminders made, and compensation provided to cover transportation costs and time. If a child does not complete his/her second cleaning within eight

months of his/her first, we will assume that he/she has voluntarily withdrawn and will inform parents that their child is no longer eligible to obtain the second dental cleaning, nor is part of the study anymore. Parents will also be reminded that there will be no penalty or impact on CHLA quality of care as a result of withdrawing or dropping out of the study.

### 7.6 Unscheduled Visit

If the child requires dental care other than routine cleaning between enrollment and completion of the study, he or she may do so at his/her regular dental provider's office (whether that is at CHLA or elsewhere). If an unrelated emergency visit before or between SADE Study dental visits occurs, we will record its occurrence and allow the participant to continue to participate in the study following review of the reason and outcome of the visit by the principal investigator and Co-I, [name]. If an unrelated visit occurs between SADE Study visits (e.g., treatment of cavities found during Visit 3), we will also record its occurrence and allow the participant to continue to participate in the study.

### 8 STUDY PROCEDURES/EVALUATIONS

### 8.1 Study Procedures/Evaluations

# **Medical History**

Medical history will be obtained from parent-report and will include diagnosis of ASD, list of current medications, and a list of any other medical diagnoses. This information will be obtained to ensure that the child participant does not meet any of our stated exclusion criteria (e.g., genetic, endocrine or metabolic dysfunction; significant motor impairment, cleft palate, taking an anticholinergic medication, etc.).

# **Prior to Dental Cleanings**

Child-Descriptor Assessments. As detailed above (Section 7.2), immediately following the consent/assent process parent- and child-report (if child is able) surveys will be completed (See CRFs 5-12, 28: Child & Family Information, CASI-Anx, SSP-2, CFSS-DS (parent), VABS-II Expressive Communication Domain, Dental History Form, Dental Care in Children Questionnaire, CFSS-DS (child), MCDASf), and SensOR. These forms will provide information about the child's sensory processing difficulties, dental anxiety, and previous dental experiences. Children with ASD will come to CHLA for an additional visit to confirm ASD diagnosis via administration of the ADOS-2 test. At this visit, the psychologist will also administer the WASI-II in order to assess child IQ.

# **During the Dental Cleanings**

Oral Care-Related Assessments. Consistent with routine practice at CHLA Dental Clinic, an oral examination (including assessment of caries, developmental defects, and general oral growth and development) will be conducted prior to each of the child's dental cleanings. The dentist will also conduct the Oral Hygiene Index-Simplified, Plaque Index, Gingival Index (OHI-S, PI, GI; located in Oral Health Indices Form, CRF 13). The first exam will take place at approximately the appropriate recall time (e.g., approximately 6 months following the last dental cleaning) for the child participant; the second will occur approximately four-six months following the first study-related dental visit. Both dental visits will include an oral examination, prophylaxis, and fluoride application.

As part of this study, a dentist blinded to the experimental conditions will also complete the Plaque Index from intra-oral photographs taken at the beginning of the cleaning and the end of the dental treatment in order to obtain further information about the oral health of the study participants. Comparison of pre- vs. post-cleaning Plaque Index scores will be included as a quality of care measure. This scoring will take place at a later time (See CRF 16: Quality of Care Recording Form).

Behavioral and Physiological Measures of Distress. Both dental cleanings will be video-recorded in their entirety, with a focus on the child's face and on the number of hands being used to restrain the child. This information will be video-coded by the research team at a later time using the Children's Dental Behavior Rating Scale (CDBRS) to gather information about overt distress behaviors exhibited during the dental cleanings. Additionally, EDA will be recorded from the child's index and middle fingers of his/her non-dominant hand. Electrodes will be placed and secured using medical tape, with recordings sent directly to a computer in the private dental room via the BIOPAC system. Like the video-recordings, these EDA recordings will be analyzed at a later time (See CRFs 22-23: CDBRS & Scored EDA Forms).

# Immediately Following the Cleanings (at CHLA)

Dentist. Following the completion of each of the two dental visits, the dentist will take additional intra-oral photographs for later scoring of quality of care. He/she will also complete the Anxiety and Cooperation Scale and Frankl Scale to report on distress behavior displayed during each cleaning (See CRF 14: Behavioral Indices Form).

Child. Following the completion of each of the two dental visits, the child (if able, and with assistance), will report on perception of pain using the Faces Pain Scale – Revised (FPS-R) and rank the degree of bother of the sensory stimuli encountered during the dental visit using the Dental Sensory Sensitivity Scale (DSSS). Additionally, following the dental visit in the SADE, children will be asked five additional questions as part of the Child SADE Acceptance Form to elicit information about whether or not they liked/enjoyed the specific adaptations made to the environment (See CRFs 17-19).

Parent. Following the dental visit in the SADE, parents will be asked to complete the Parent SADE Acceptance Form to elicit information about how they felt themselves about the SADE adaptations and whether or not they perceived that these adaptations helped make their child's experience better (See CRF 20).

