# 3.2.2 Outcome Measures for the Secondary Objectives

Our secondary outcome measures will consist of five behavioral indicators of distress (observational coding of behavioral distress from video-recordings, dentist-reported measures of child anxiety and cooperation, child self-report of pain, and child self-report of discomfort with sensory stimuli), measures of mediating factors, measures of moderating factors, and measures of cost-savings and quality of care.

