#### 7.2 Enrollment/Baseline

# **Enrollment Visit (Visit 1, Day 0)**

- Further explain study protocol and participant responsibilities in greater detail than that discussed on the screening for eligibility phone call. Answer any parent or child questions.
- Verify inclusion/exclusion criteria.
- Obtain and document consent from parent on study consent (parental permission) form. Explain and obtain signature from parents on study HIPAA form.
- Explain and provide parents with California Bill of Rights.
- Obtain and document child assent from child subject on study assent form (if child is available and able to complete/understand form).

• Parental completion of the Parent Bilingual Questionnaire to assess the child and parent's bilingual preference (see Appendix N in MOP).

- Use the Decision Tree for Accepting Child's Data as a guideline to determine if the child is able to give assent based on the parent report (see Appendix O in MOP).
- Parental completion of study questionnaires to obtain demographic information, dental history, anxiety, and sensory over-responsivity. (Complete list of measures to be completed are listed in the Schedule of Events in Appendix A; see CRFs 5-10, 28: Child & Family Information (Demographics), CASI-Anx, SSP-2, SensOR, CFSS-DS, VABS-II Expressive Communication Domain, Dental History Form, Dental Care in Children Questionnaire)
- Child completion of study questionnaires (if able) to obtain information about child perception of dental anxiety. (Complete list of measures to be completed are listed in the Schedule of Events in Appendix A; see CRFs 11-12: CFSS-DS, MCDASf)
- Parents are shown and instructed in the use of the specialized study social story for going to the dentist and participating in the SADE study. Parents are informed that the social story will be mailed to them with instructions two weeks prior to the child participant's first (and second) dental cleaning.
- Parents and children are shown the EDA electrodes and allowed to play with them.

*Note:* This visit (Visit 1) will take place at the participant's home, or if the family prefers, at CHLA, prior to the Autism Diagnostic Confirmation Visit (Visit 2).

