# 12.4 Final Analysis Plan

Descriptive statistics will be performed for all variables of interest to describe the participant population at baseline, including attrition rate and missing data, to compare those randomized to SADE first vs. those randomized to RDE first. We anticipate a low attrition rate (~10%) and will impute missing data for intent-to-treat analyses using Markov Chain Monte Carlo (MCMC)

imputation with multiple values imputer for each missing value averaged for an estimation for analyses. Bivariate associations between outcomes (physiological anxiety and children's negative behavioral responses), environment (SADE or RDE), and covariates (age, gender, order of visit, autism severity, IQ, and sensory sensitivity) will be described. The primary objective of determining difference between dental environments will be tested using intent-to-treat models examining the within-subject factor of dental environment (SADE vs RDE) using repeated measures ANCOVA for each outcome. *A priori* covariates include age (continuous), randomized order of visit, gender, and temperature. Other participant characteristics that are unbalanced between order of visits will be included as covariates *ad hoc*.

The secondary objective of examining the mediating effect of physiologic response on behavioral outcomes will be tested by first examining the bivariate relationships between EDA and behavioral outcomes, and then adding EDA estimates (SCL and NS-SCR) to models of dental environment difference on behavioral outcomes, and examining the change in the within group coefficients. A change in coefficient >15% will be considered evidence of mediation. While we have several outcomes, we specify only one mediator, thus we will apply a rational approach to examination of multiple outcomes, and will assess the fidelity of our study by estimating effect sizes (Cohen's d) of the dental environment before and after the mediation factors are assessed to confirm that statistical results were supported by clinical relevance of findings. If physiological anxiety does mediate the environment's effect on negative behavioral responses, we anticipate that the anticipated effect of environment will be eliminated once we add in EDA to the models specified in Hypothesis 2. Analyses will be performed using SPSS (v.22); a priori two-sided  $\square = 0.05$ .

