# **Primary Objective: Hypothesis 1**

The primary objective is to test the effect of the environment (SADE vs RDE) on physiological anxiety. Hypothesis 1 specifies an effect of environment on the outcome, thus the main effect of interest will be  $B_1$ , the dental environment.

Hyp 1: EDA =  $B_0$  +  $B_1$ \*Environment + Covariates

## Secondary Objective 2: Hypothesis 2

The secondary objective explores further outcomes and mechanisms of the group differences. Hypothesis 2 is analogous to those in the primary aim and have the same coefficients of interest. However, there are multiple, secondary outcomes including behavioral distress, perception of pain, and sensory discomfort). As noted above, we will apply a rational approach to examination of multiple outcomes and will assess effect sizes of the coefficients, in addition to the statistical significance.

Hyp 2: Negative behavior =  $B_0 + B_1$ \*Environment + Covariates

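### The imputation rule in Section 12.4 does not exempt children who cannot self-report pain or sensory discomfort, and averaging the draws would treat their filled-in scores as measured

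*Combined protocol and SAP*

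**What the plan says.** Section 3.2.2 lists "child self-report of pain, and child self-report of discomfort with sensory stimuli" among the secondary outcomes. Section 8.1, under the procedures immediately after each cleaning, makes both scales conditional: "the child (if able, and with assistance), will report on perception of pain", with the DSSS in the same sentence.

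The protocol expects some children to be unable. Section 7.2 makes the child questionnaires conditional on ability and refers to a Manual of Procedures tool, the Decision Tree for Accepting Child's Data, used "to determine if the child is able to give assent based on the parent report". Section 15.3 provides for children whose cognitive abilities prevent assent. Sections 5.1 and 5.2 set no IQ or language-level limit for the child, and Section 5.3 seeks a wide range of ASD severity.

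On missing data, Section 12.4 opens with "We anticipate a low attrition rate (~10"%) and goes on to say that the team "will impute missing data for intent-to-treat analyses using Markov Chain Monte Carlo (MCMC"), described as "imputation with multiple values imputer for each missing value averaged for an estimation for" analyses. The models are intent-to-treat, "using repeated measures ANCOVA for each outcome", and for pain and discomfort "Hypothesis 2 is analogous to those in the primary aim and have the same coefficients of interest". No outcome and no reason for missingness is set apart, and no analysis set for self-reported outcomes is defined.

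**The concern.** A child who cannot use the scales has no FPS-R or DSSS value at either visit. This differs from a dropout or a skipped form, where a score could have been given and the child usually has one at the other visit. Two problems follow if the rule is applied as written.

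First, the target is undefined. The plan does not say whether the pain and discomfort effect is meant for all randomised children or for those able to report. Filling in the rest means carrying over results from more able children, with little or no overlap in the region where the scales go unused.

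Second, reducing several draws to one averaged value removes the uncertainty that multiple imputation is meant to carry. The sample size is counted as full while the information comes from fewer children, so p-values and intervals for Hypothesis 2 on these outcomes would be too favourable. The Hypothesis 4 models for these outcomes, which test IQ and ASD severity as moderators, would lean on the same filled-in values.

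**Working it through.** **Inputs.** N with repeated measures: 165 (Section 12.2). Test level: two-sided 0.05 (Section 12.4). Pilot effects: d = 0.69 for sensory discomfort and 0.62 for pain (Section 12.2). Share unable at both visits, f: not in the documents, so 10 to 40% is assumed. Number of draws m: not stated, so 20 is assumed.

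**The plan's own figure.** For a paired comparison with d = 0.22, 80% power and two-sided 0.05, the normal approximation is n = ((1.960 + 0.842)/0.22)², which rounds up to 163. The exact t version gives 165, with power 0.802. So 165 reproduces, but only if all 165 children supply scores. Nothing is set aside for inability to report.

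**Effect of averaging.** Let σ be the SD of the within-child SADE minus RDE difference. The averaged imputed differences sit close to the mean of the able children.

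- The estimate carries the information of N(1−f) children, so its true standard error is about σ/√(N(1−f)).
- The analysis uses all N values, but their variance has shrunk to about σ²(1−f), so the computed standard error is about σ√(1−f)/√N.
- The ratio of computed to true standard error is therefore about 1−f.
- The actual type I error is about 2[1 − Φ(1.96(1−f))]. N cancels, so the result depends on the share unable and not on whether 165 or 220 is used.

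Simulation with no effect, N = 165, both visits missing, 20 draws averaged and no covariates:

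| Share unable | Computed/true SE | Type I error, formula | Type I error, simulated runs |
|---|---|---|---|
| 10% | 0.90 | 0.078 | 0.076–0.078 |
| 20% | 0.80 | 0.117 | 0.109–0.117 |
| 30% | 0.70 | 0.170 | 0.163–0.169 |
| 40% | 0.60 | 0.240 | 0.234–0.236 |

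Five draws instead of 20 give similar values (0.074, 0.112, 0.165, 0.223).

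**What causes it.** In the same setting, analysing only the able children gives about 0.05 at every share. So does multiple imputation of everyone with between-imputation variance included (0.053, 0.048, 0.047, 0.052). The inflation therefore comes from averaging. Because the simulation has no true effect and treats able and unable children alike, it says nothing about bias.

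**Cost of restricting to able children** (N rounded down, 80% power, two-sided 0.05):

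| Share unable | N | Detectable d | Power at d = 0.22 | Power at d = 0.62–0.69 |
|---|---|---|---|---|
| 10% | 148 | 0.232 | 0.76 | >0.99 |
| 20% | 132 | 0.246 | 0.71 | >0.99 |
| 30% | 115 | 0.263 | 0.65 | >0.99 |
| 40% | 99 | 0.284 | 0.58 | >0.99 |

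**The case against.** The strongest reply is that imputation was meant for dropouts only. The sentence that introduces it begins with the attrition rate, so that reading is plausible. The Decision Tree's title also suggests a rule on whose answers are accepted, and the Manual of Procedures was not available for this review. Both points stand as reasons to ask for clarification. Neither settles the matter: Section 12.4 speaks of each missing value and each outcome without exception, and the only use that Section 7.2 gives for the tree is judging ability to assent.

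A second reply is that averaging, not inability, drives the error rates. That is correct. Averaging would also distort results for ordinary one-visit dropout on any outcome. What inability adds is a block of children missing at both visits, possibly well above the anticipated 10%, and an unanswered question about whom the result describes.

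A reader might infer that these data are missing not at random, or that the scores would simply be made up. The documents do not establish either. IQ, ASD severity and expressive communication are all measured (Section 3.2.2, child-descriptor table), as are behavioural and electrodermal outcomes that need no self-report. All could enter the imputation model, whose variables are not listed. The supportable statement is poor overlap and an undefined target population. Nor can one say that the scores come only from verbal children: the FPS-R is a single item with six faces, it is given with assistance, and no section requires speech.

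**Conclusion.** The concern holds as a gap in Section 12.4. Applied as written, the rule fills in FPS-R and DSSS scores for children with no self-report at either visit and analyses them as measured. With 10, 20, 30 or 40% of 165 children unable, the nominal 5% test rejects about 8, 11, 16 to 17 or 23% of the time under no effect, and standard errors are too small by roughly the share unable.

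These figures rest on an assumed share, an assumed number of draws, a model without covariates, and the literal reading of the imputation sentence. They measure false precision. A reader might take them as the bias from children's inability to report, but the size and direction of that bias cannot be derived from the documents.

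The reach is two secondary outcomes under Hypothesis 2 and the moderator models on them, which the plan itself calls exploratory. The electrodermal primary outcome does not depend on self-report and is not touched by this point. The change should be made but is not critical to the trial's main conclusion.

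**What to change.** In Section 12.4:

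1. Define the FPS-R/DSSS analysis set as children judged able to self-report, by a rule applied before the first cleaning and blind to sequence. State whether the Decision Tree for Accepting Child's Data is that rule. Section 7.3 (COVID-19 note) records that all participants had completed Visits 1 to 3 by March 2020, so the classification has to rest on records made before Visit 3.
2. Do not impute FPS-R or DSSS for children outside this set.
3. Report the number unable by sequence, and limit the pain and discomfort conclusions, including moderator findings on them, to this set. CDBRS and the dentist ratings remain the behavioural outcomes for the whole sample.
4. For able children with a missed form or visit, analyse each imputed data set and combine the results with between-imputation variance, instead of averaging draws into one value.

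The cost is SAP wording, a narrower claim and a smaller N: 148 to 99 at 10 to 40% unable. Power at the pilot effects stays above 0.99. It would fall to between 0.76 and 0.58 if the true effect were only d = 0.22.
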